Population	Sample size is 80 enrolled subjects, 40 at UTHealth Houston, 40 at Penn. Participants will be females ages 18-45 with chronic (at least 1 month post-trauma) DSM-5 FULL PTSD diagnosis and a Clinician-Administered PTSD Scale for DSM-5 (CAPS) Past Month version score ≥ 20 OR chronic (at least 1 month post-trauma) subPTSD diagnosis and CAPS Past Month version score of ≥ 20 (subPTSD defined as: meeting criterion A, F, G, H, and clusters B, C, and at least 1 of the clusters D or E.). Trauma needs to fall under Criterion A. Participants will be on stable medications (for 3 or more months by the time of study entrance), outpatient, and will provide informed consent. For naturally cycling female subjects, stage of menstrual cycle will be ascertained by history, and by serological measures. For women on oral contraceptives, we will identify those using monophasic or biphasic of first, second, third or fourth generation with up to 35mcg of ethinyl estradiol.

Study Sites	UTHealth Houston [REDACTED]
	[REDACTED] University of Pennsylvania Perelman School of Medicine
	[REDACTED]
Number of participants	80 participants expected to be enrolled across 2 sites
Description of Study Agent/Procedure	Study drug will consist of one 2.0 mg dose of estradiol, (obtained from Estrace® Tablets, 2.0 mg estradiol tablets, USP, Warner Chilcott [now Allergan, as Warner Chilcott was acquired by Allergan]) taken orally.
Reference Therapy	Placebo
Key Procedures	Pregnancy Test, Urine Toxicology Screen, fMRI scan, Blood Draw, Estradiol/Placebo Dosage
Statistical Analysis	For all aims, analyses of SCR will test for group x condition interactions for the different groups in each aim with respect to CS+E vs. CS+U. With respect to the fMRI data, the initial analysis will involve assessing for a main effect of group (E vs. Plc), post treatment using CS+E vs. CS+U contrast. In addition, we will compare post treatment brain activations vs. pre-treatment within each group as well as the interactions between time and group also using the same imaging contrast.

Schematic of Study Design

Process Diagram

Visit 0: Telephone Screening

- Local advertising efforts instruct prospective participants to complete a screener
- The Research Assistant/study team member at UTHealth Houston calls and screens individuals for eligibility based off of the screener. Such screening is routine at UTHealth Houston and requires about 30 minutes.

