3.1 Primary Objective

The primary objective is to delineate the influence of exogenous administration of estrogen on conditioned responses during extinction recall in women with PTSD.

Specific Aim 1.1: To examine the effects of E2+PE on the extinction-induced psychophysiological responses (SCR), neural responses, and the information flow between the fear extinction nodes at post-PE sessions relative to pre-PE.

Hypothesis 1.1: During extinction recall, both groups will show lower SCR at post- relative to pre-PE. A general improvement is expected over time in both groups given the anticipated benefits of PE alone. However, we expect a significant Time x Group interaction, where the Estradiol-treated group should exhibit significantly lower fear levels (indexed via SCR) at the follow-up assessment relative to the Placebo group. 2) For both groups, extinction recall-induced activations will be higher in brain regions associated with extinction learning and recall (i.e. vmPFC and hippocampus) and lower in regions associated with fear expression (i.e. dACC and amygdala) at post- relative to pre-treatment. Note that a general improvement from pre to post is expected in both groups, given the anticipated benefits of PE alone. We do expect, however, a significant

Time x Group interaction, with most pronounced effects at post-PE in the estradiol-treated group. 3) Information flow between the extinction nodes will improve (indexed by DCM models), with stronger effects in E2+PE after treatment.

Specific Aim 2: To examine the impact of E2 administration on PE efficacy at reducing PTSD symptom severity.

Hypothesis 2: PTSD symptom severity will be significantly lower in the E2+PE group relative to the Placebo+PE group following acute treatment, as well as at the 3- and 6-month follow-up assessments.

Specific Aim 3: To test the interaction between E2+PE induced psychophysiological and neuronal changes (pre-to-post) with the improvement of PTSD symptom severity.

Hypothesis 3: PTSD symptom reduction will correlate with BOLD and SCR changes observed during extinction recall following PE.

4 Study Design and Endpoints

Section 4 will provide a brief overview of the phases of the clinical protocol (screening, baseline, experimental days). More details on procedures occurring during each phase will be included in subsequent sections of the protocol.

Therapist Training Procedures:

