9.2 Statistical Hypotheses

Hypothesis 1: Compared to the placebo-PE group (Plc+PE): 1) the E2+PE group will exhibit faster reduction of SCR between PE sessions, and 2) after 5 E2+PE sessions, the extinction recall deficit indexed by elevated SCR during extinction retention test will be rescued (i.e., SCR in the E2+PE group will be significantly lower

relative to the Plc+PE group). 2) Extinction-induced activations will be higher in the vmPFC and lower in the dACC and amygdala in post relative to pre E2+PE treatment. When comparing E2+PE vs. Plc+PE, similar differences are expected, but to a lesser degree given the anticipated benefits of PE alone.

Hypotheses 2: PTSD symptom severity will be significantly lower in the E+PE group relative to the Plc+PE group following treatment, as well as at the 3 and 6-month follow-up assessments.

Hypothesis 3: The degree of PTSD symptom reduction post- compared to pre-PE will be associated with BOLD changes in the fear extinction network and reduction in SCR during the extinction recall test after PE. The magnitude of BOLD and SCR changes will be significantly larger in the E2+PE group compared to the Plc+PE group.

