9.3 Analysis Datasets

The proposed experiments in this project are aimed to examine the effects of E2+PE on the extinction-induced SCR and neural responses at post-PE sessions relative to pre-PE. SCR will be recorded as a psychophysiological index of fear extinction and extinction recall. We will conduct standard fMRI analyses to examine information flow changes in the extinction network. These data will test hypothesis 1 stated above.

Another objective of the project is to examine the impact of E2 administration on PE efficacy at reducing PTSD symptom severity. Here, we will use all clinical data (CAPS) before and after treatment as well as 3, 6 months follow up data. These data will be used to test hypothesis 2 stated above.

The combined data sets will then be used to test hypothesis 3 above.

Primary analyses will be based on a modified intent to treat sample including all participants who took at least one dose of the study medication.

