9.4 Description of Statistical Methods

9.4.1 General Approach

Statistical Methods

SCR Analyses

For all experimental phase, SCR will be computed for each trial by subtracting the mean skin conductance level observed during the last two seconds of context presentation from the maximal skin conductance level reached during CS presentation. All SCR values will be square-root transformed prior to any statistical analyses. To evaluate extinction recall, an extinction retention index (ERI) will be computed for each individual using the following formula: $100 - (\text{mean SCR to the first 4 CS+E trials during recall} / \text{maximum SCR reached during conditioning for this same cue}) * 100$.

Functional MRI analysis

The specific emphasis of the fMRI analysis will be on the extinction recall phase (first four trials of the CS+E vs. first four trials of the CS+U contrast). This contrast has been chosen given the literature demonstrating a significant deficit of PTSD patients during that specific phase of the experimental protocol. BOLD signal will be extracted from the four ROIs (amygdala, dACC, vmPFC and hippocampus). For each of these ROIs, we will use mixed model ANOVAs with time (pre vs. post PE) and group (E2+PE vs. Plc+PE) to investigate main effect of each of these variables as well as group by time interaction. Whole-brain analyses will also be conducted as supplemental analyses for the sake of completeness. We will also conduct regression analyses comparing the change in BOLD responses in each of our ROIs from post- to pre-treatment with PTSD symptom reduction in each of the two groups (E2+PE and Plc+PE).

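### Aim 3 is analysed by separate regressions in each arm, so no planned model estimates the brain-change/symptom association in all patients or compares it between arms

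*Combined protocol and SAP*

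**What the plan says.** Section 3.1 states Aim 3 as "To test the interaction between E2+PE induced psychophysiological and neuronal changes (pre-to-post) with the improvement of PTSD symptom severity". Its hypothesis there is an association: "PTSD symptom reduction will correlate with BOLD and SCR changes observed during extinction recall following PE". Section 9.2 restates Hypothesis 3 as an association of symptom reduction with BOLD and skin conductance (SCR) changes, and adds: "The magnitude of BOLD and SCR changes will be significantly larger in the E2+PE group compared to the Plc+PE group". The Protocol Summary ranks this objective as tertiary.

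The only analysis that links brain change to symptoms is the last sentence of the fMRI paragraph in Section 9.4.1. It compares BOLD change in each region with "PTSD symptom reduction in each of the two groups (E2+PE and Plc+PE". The regions are listed just before: "BOLD signal will be extracted from the four ROIs (amygdala, dACC, vmPFC and hippocampus".

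Other statements come close but do not fill the gap:

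- Section 9.4.1 plans a mixed-model ANOVA per region "to investigate main effect of each of these variables as well as group by time interaction". It contains no symptom variable.
- The Protocol Summary says that "analyses of SCR will test for group x condition interactions for the different groups in each aim". Condition there means CS+E against CS+U, not symptom change.
- Section 9.3 says: "The combined data sets will then be used to test hypothesis 3 above". That names the data, not a model, and does not say that the arms are analysed together.
- Section 9.4.6 plans GEE or mixed models for treatment differences over the assessments, not for the link between BOLD and symptoms.

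No regression of symptom reduction on SCR change is described anywhere, although both statements of Hypothesis 3 include SCR.

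**The concern.** Two separate within-arm regressions serve neither reading of Aim 3 well. If the aim is a plain association, as the hypothesis in Section 3.1 says, splitting the sample halves the number of patients behind each test. If the aim is an association that differs by arm, two within-arm p-values do not test it: one may fall below 0.05 and the other above it when the true slopes are identical.

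The second problem matters most in a trial about mechanism. A significant slope under estradiol beside a non-significant one under placebo invites a claim of an estradiol-specific mechanism, and nothing in the plan would check it.

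**Working it through.** **Inputs from the documents.** Section 9.5: 80 patients, about 20% unusable data, about 20% dropout, 50 complete data sets, 25 per group, alpha 0.05. Section 9.4.1: four regions, two arms.

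**The plan's own figures.** 80 × 0.8 × 0.8 = 51.2 and 80 × (1 − 0.4) = 48, so 50 complete sets is consistent. The stated 85% power concerns a between-group difference and cannot be reproduced, because no effect size is given. At 25 per arm it implies a standardised difference of about 0.865 (two-sided t-test). No power is stated for Aim 3.

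**Assumptions.** Two-sided 0.05; true correlation r, equal in both arms unless stated. The documents give no r, so a range is shown.

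**Step 1, power for an association.** Fisher's z: power ≈ Φ(atanh(r) × √(n − 3) − 1.96). For r = 0.4, atanh(r) = 0.4236:

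- n = 25: 0.4236 × √22 = 1.987, so Φ(0.027) = 51%.
- n = 50: 0.4236 × √47 = 2.904, so Φ(0.944) = 83%.

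**Step 2, chance that exactly one arm is significant when the slopes are equal.** With per-arm power p, this is 2p(1 − p).

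| r, both arms | Per arm, n = 25 | Pooled, n = 50 | At least one arm significant | Exactly one arm significant |
|---|---|---|---|---|
| 0.3 | 30.6% | 56.4% | 51.8% | 42.5% |
| 0.4 | 51.1% | 82.8% | 76.1% | 50.0% |
| 0.5 | 73.1% | 96.5% | 92.8% | 39.3% |
| 0.6 | 90.2% | 99.7% | 99.0% | 17.7% |

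If the two within-arm z values are combined instead (√44 in place of √47), pooled power for r = 0.3, 0.4 and 0.5 is 53.7%, 80.2% and 95.4%; the conclusion is the same. A simulation with 4,000 runs per setting gave common-slope power of 56%, 83% and 97% for those r, exactly one significant arm in 43%, 49% and 37% of runs, and a significant interaction in about 5%, as it should be.

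The smallest r detectable with 80% power is tanh((1.96 + 0.84)/√22) = 0.54 per arm and tanh((1.96 + 0.84)/√47) = 0.39 pooled.

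**Step 3, fewer complete sets.** Section 9.5 gives the 20% unusable data as applying at each of two time points. If those losses are independent, 80 × 0.8³ = 41 sets remain. At r = 0.4, power is then 42% per arm (n = 20) against 74% pooled (n = 41).

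**Step 4, power to compare the arms.** Difference of two z values, standard error √(2/22) = 0.302.

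| True r in the two arms | Interaction power |
|---|---|
| 0.5 and 0 | 44% |
| 0.6 and 0.2 | 37% |
| 0.5 and 0.2 | 21% |

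Reaching 80% power needs about 0.69 against 0.

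**Step 5, association in one arm only (0.5 and 0).** In simulation, the within-arm test in that arm has about 75% power, the common slope 43% and the interaction 44%.

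**The case against.** The strongest reply is that the documents never clearly promise a comparison of slopes. Aim 3 does use the word interaction, and a reader might infer that an arm-by-change test was promised and then left out. The text does not support that: the aim names physiological change and symptom improvement as the two terms, and its own hypothesis asks only for a correlation.

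A reader might also infer that the between-group sentence of Hypothesis 3 in Section 9.2 goes untested. It concerns the mean size of the changes, not their relation to symptoms, and for BOLD the group-by-time ANOVA tests it. That sentence is not part of this defect.

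It can also be said that a common association would often show up somewhere. At r = 0.4, at least one arm is significant 76% of the time, against 83% pooled. That is fair, but two unadjusted tests carry a false-positive rate of 1 − 0.95² = 9.8%, so the comparison is not like for like.

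If the association exists only under estradiol, the within-arm test is the more powerful one (Step 5). This stands as a real cost of pooling. It does not rescue the inference, since a within-arm result cannot show that the arms differ.

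Finally, no section says that significance in one arm alone will be interpreted as a mechanism. That is a risk of the design as written, not a stated intention.

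**Conclusion.** The point holds in a limited form. As worded, the Aim 3 regressions are per arm, and nothing planned estimates the association in the whole evaluable sample or compares it between arms. If one model was intended, the text does not say so.

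What is lost is half the sample per test. It is tempting to call this half the power, but the loss depends on r: about 26 points at 0.3, 32 at 0.4, 23 at 0.5 and 10 at 0.6. With equal slopes and r between 0.3 and 0.5, exactly one arm is significant in about 39% to 50% of trials.

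These figures rest on assumed correlations, 25 evaluable patients per arm and a simple correlation in place of the full covariate model. The aim is tertiary, and the planned BOLD treatment comparison is unaffected. The change is still worth making, because it is cheap and the per-arm wording answers the aim poorly under either reading.

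**What to change.** Replace the per-arm sentence in Section 9.4.1 with one model per region on all evaluable patients: post-treatment CAPS-5 Past Week score on baseline CAPS, arm and BOLD change, with severity stratum (Section 7.1.3) and site. Then:

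- test Hypothesis 3 with the common slope, from the model without an interaction;
- add arm × change and report it as an estimate with its confidence interval;
- show within-arm slopes descriptively;
- fit the same model with SCR change, which Hypothesis 3 includes and Section 9.4.1 does not relate to symptoms.

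Also state how the four regions are handled. The main BOLD tests fall from eight to four, but if independent at 0.05 they still carry a familywise error of 1 − 0.95⁴ = 19% (34% for eight).

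The cost is a short paragraph and one added SCR analysis, written before the blind is broken; no new data are needed. There are three limits. The interaction will be imprecise (about 20% to 45% power for the differences in Step 4). The common slope gives up power if only one arm has an association. The model also carries several covariates on 41 to 50 patients; if that is too many, the severity stratum is the natural one to drop, since baseline CAPS already carries most of that information.

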9.4.2 Analysis of the Primary Efficacy Endpoint(s)

Details of the analyses for the primary efficacy endpoints are provided above in sections 10.1, 10.2, and 10.3.

9.4.3 Analysis of the Secondary Endpoint(s)

Details of the analyses for the secondary efficacy endpoints are provided above in sections 10.1, 10.2, and 10.3.

9.4.4 Safety Analyses

See Protection against risks and safety assessments under procedures above.

Participants' reactions to study assessments and treatment will be closely monitored, and negative reactions will be addressed therapeutically. Participants could develop mild to moderate emotional discomfort or frustration associated with psychiatric interviewing or filling out questionnaires. Participants will be allowed any breaks in the testing that are needed. Any events related to safety during assessment period will be documented as they occur.

PE is considered very safe and therefore risks associated with its delivery are mild to moderate. Patients might experience discomfort when exposed to anxiety-provoking images and situations in treatment sessions and at home for homework and discomfort about being in treatment for victims of a traumatic event. Based on our extensive experience in PE, only a handful report negative side effects from it. None of the participants in our past or most recent treatment studies, sustained prolonged negative reactions to exposure. Any negative events associated with PE will be documented as they occur.

Regarding safety analyses associated with Estradiol use, common side effects of chronic administration of this drug include headache, breast pain, irregular vaginal bleeding, stomach cramps, nausea, or hair loss. As noted above, there are no known side effects of acute single doses of estrogen, as it is the case in the current application. All of the women to be recruited will already be using oral contraceptives. A total of 5 doses over 3 weeks will be administered for this study. These acute E2 doses do not pose a significant risk for the participants. To assess for safety, at each PE appointment, participants will be asked how they are feeling and if they had encountered any of the potential side effects. If that is the case, these will be documented and reported. An MD from our study staff will discuss and review the symptoms with the participants and a clinical decision will be made whether or not the subject should stop her participation in the study.

9.4.5 Adherence and Retention Analyses

The adherence to the protocol will be noted based on the absence or decision made by participants not complete the study procedures during the 6 PE sessions. Adherence to medication consumption will be assessed based on the subjective reports of the participants. Note that while blood samples will be collected to measure hormonal levels in our participants, these cannot be used to analyze adherence given that some participants will be using the placebo pills and thus no change in serum estradiol would be expected.

9.4.6 Baseline Descriptive Statistics

We will perform descriptive statistics prior to testing our hypotheses. These statistics will include means (or frequencies and proportions for categorical variables), standard deviations, skewness and kurtosis, and odds-ratios. Variables with distributions violating assumptions of normality will be transformed. If this fails to improve the normality of the distribution, distribution-free statistics will be employed. This study has baseline, post-treatment, and two follow-up assessments, creating clustered data due to repeated measures. Thus, we will use established methods for such study designs to examine treatment differences, including the two most popular approaches for longitudinal data modeling: the generalized estimating equations (GEE) and linear mixed-effects model approach (LMM). We will apply these models for both the intent-to-treat and completer analyses. Inference based on GEE or LMM is valid provided that missing data are non-informative or "missingness" does not depend on the value of the unobserved outcome. Although missing data in many studies in mental health research are non-informative, we will perform sensitivity analyses to ensure that this is the case. In particular, we will entertain both parametric and semi-parametric models that assume some missingness mechanism and compare estimates obtained from such models with those from GEE and LMM. Such analyses will inform us whether the non-informative missingness assumption is violated and if so, to what extent. If the non-informative missingness assumption is deemed to be severely violated, we will report treatment effects using the methods that account for informative missingness.

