5.1 Inclusion Criteria

In order to be eligible to participate in this study, an individual must meet all of the following criteria:

1. Female, 18-45 years of age
2. Chronic (at least one month post-trauma) DSM-5 FULL PTSD diagnosis **OR subPTSD** diagnosis (subPTSD defined as: meeting criterion A, F, G, H, and clusters B, C, and at least 1 of the clusters D or E.)
3. CAPS-5 Past Month score ≥ 20
4. Criterion A traumatic event
5. Stable medications for 3 or more months by the time of study entrance (with the exception of benzodiazepines)
6. Women on oral contraceptives, specifically those using monophasic or biphasic of first, second, third or fourth generation with up to 35mcg of ethinyl estradiol; OR using etonogestrel / ethinyl estradiol 0.120mg/0.015mg per day vaginal ring birth control; OR using the norelgestromin / ethinyl estradiol 0.150mg/0.035mg per day transdermal patch birth control.
7. Willing and able to provide informed consent

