9.4.9 Efficacy Review

Interim analyses will not be conducted. All analyses will be conducted after breaking the blind at the end of the study unless a blinded review is requested by the DSMB.

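### Section 9.4.6 lets a variable's observed distribution, rather than model residuals, decide its scale and test, and that choice can be made after unblinding

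*Combined protocol and SAP*

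**What the plan says.** Section 9.4.6 opens with "We will perform descriptive statistics prior to testing our hypotheses." It then gives a two-step rule. First, "Variables with distributions violating assumptions of normality will be transformed." Second, "If this fails to improve the normality of the distribution, distribution-free statistics will be employed." The same paragraph goes straight on to the treatment comparison over the baseline, post-treatment and two follow-up assessments. It names GEE and the linear mixed model (LMM) and makes neither primary.

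Section 9.4.9 fixes the timing: "All analyses will be conducted after breaking the blind at the end of the study unless a blinded review is requested by the DSMB."

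Section 9.4.1 settles part of the matter for the primary endpoints. "All SCR values will be square-root transformed prior to any statistical analyses," and a mixed model ANOVA with time and group is named for each BOLD region. Nothing there exempts SCR or BOLD from the rule in 9.4.6.

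No other section fills the gap. Sections 9.4.2 and 9.4.3 refer to Sections 10.1 to 10.3, and 9.4.10 refers to 10.4.6, but Section 10 deals with source documents. If 10.4.6 is read as 9.4.6, this paragraph is the stated analysis plan. For CAPS it is the only place that names a treatment-effect model.

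**The concern.** The rule looks at the wrong object. A linear mixed model makes assumptions about residuals and random effects, and GEE does not assume normal outcomes. A skewed or bounded variable is therefore no reason in itself to abandon either.

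The steps that follow are open. The transformation is unnamed, and for SCR it would be a second one on top of the square root. The distribution-free method is also unnamed. Hypothesis 1.1 in Section 3.1 rests on a Time x Group interaction, and CAPS has four assessments. A simple rank test of post-treatment values neither estimates that interaction nor uses the repeated measures. A transformed CAPS result would also leave the point scale on which the trial states its own criteria (30% improvement and a score of 26, Section 7.1.2).

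Finally, the choice can be made with the arms known. Even if it is made honestly, a reader of a positive result could not tell that it was.

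**Working it through.** **The plan's own figure.** Section 9.5 gives 85% power with 25 per group at alpha 0.05 and no numerical effect size, so it cannot be reproduced. Solving backwards, two-sided normal approximation: d = (1.960 + 1.036)/sqrt(25/2) = 0.85 (0.87 with the t distribution). It concerns SCR and BOLD, and this point does not depend on it. Section 9.5 gives no CAPS mean, SD or power, so every CAPS input below is an assumption.

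**1. Type I error.** 25 per arm (Section 9.5), no treatment effect, 6,000 simulated trials per outcome shape. The rule is read as: Shapiro-Wilk at 0.05 on the pooled outcome; raw t-test if passed, otherwise square-root t, otherwise log t, otherwise Mann-Whitney. Best of four takes the smallest of those p-values.

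| Assumed outcome shape | Rule fires | Raw t | Mann-Whitney | Rule followed | Best of four |
|---|---|---|---|---|---|
| Normal (mean 25, SD 10, floor 0) | 4.0% | 4.4% | 4.0% | 4.3% | 6.1% |
| Mild skew (gamma, shape 6) | 49.8% | 4.5% | 4.2% | 4.6% | 6.0% |
| Strong skew (gamma, shape 2) | 94.6% | 4.9% | 4.7% | 5.0% | 7.0% |

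Simulation error is about sqrt(0.05 x 0.95/6,000) = 0.3 points. Raw t and Mann-Whitney reached different conclusions in 1.8-3.1% of these null trials.

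**2. How often the rule fires for CAPS.** The entry criterion is "CAPS-5 Past Month score ≥ 20," whereas the endpoint is the Past Week version after treatment (Section 4.2.2). The two must be simulated separately. Assumptions: entry score normal with mean 20-40 and SD 8-12 before the cut at 20; score range 0-80; baseline Past Week correlated 0.5 or 0.8 with entry; post-treatment correlated 0.5 with entry, mean fall 12, floor 0; no treatment effect; 3,000 trials per setting. Proportion failing Shapiro-Wilk at 0.05:

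- Past Month entry score (N=80): 10% to over 99% (81% at mean 30, 37% at 35, 10% at 40, all SD 10).
- Past Week baseline (N=80): 5-14%.
- Past Week post-treatment (N=50): 4-6% at assumed means of 30 or more, 21% at 25, 69% at 20.
- Change score (N=50): 4-7%.

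The post-treatment rate rises only where scores collect at 0. A second set of assumptions (n=64, entry N(30, 11) cut at 20, post SD 12, mean fall 12 or 18) gave 9-97% for post-treatment Past Week. In one such run it was 12-13% without a treatment effect and 36-43% with one (fall 12), and about 72% and 97% (fall 18). So whether the rule fires can itself depend on the treatment effect.

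**3. Power.** n = 80 x 0.80 = 64 after the 20% dropout in Section 9.5; effect 0.5 SD, that is 0.5 x 12 = 6 points; pre-post correlation 0.5 or 0.6; other inputs as in the second set above.

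| Analysis of post-treatment CAPS | Power |
|---|---|
| Linear model with baseline | 60-68% |
| Rank-based model with baseline | 57-65% |
| Unadjusted t-test | 50-54% |
| Mann-Whitney, no baseline | 49-52% |

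Setting by setting, a Mann-Whitney test without baseline loses about 10-18 points against the baseline-adjusted linear model. A rank method that uses baseline loses about 2-3. From the ends of the ranges, dropping baseline alone costs 60 - 50 = 10 to 68 - 54 = 14 points, and moving from t to Mann-Whitney adds only 50 - 49 = 1 to 54 - 52 = 2. Repeat runs moved these figures by up to about five points without changing the pattern. Across the runs, the linear model's type I error was 4.1-5.7% despite the floor.

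**The case against.** Section 9.4.6 is headed as baseline descriptive statistics, so the rule might cover only descriptive variables, and nothing says outright that it displaces the models named in 9.4.1 or later in the same paragraph. But the text speaks of variables in general, ties the step to hypothesis testing and runs into the treatment-effect models. At best its scope is unclear, which the same edit would cure.

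The timing comes from reading 9.4.6 with 9.4.9. Section 9.4.6 does not mention the blind, and skewness can be inspected on pooled data. That stands: the plan permits an unblinded choice but does not require one.

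A distribution-free fallback need not be weak. A rank model with baseline loses little, and Mann-Whitney on change scores reached 52-64% power in these simulations. That stands too, but the plan names neither.

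Three stronger readings might be inferred, and the documents support none of them. The first is that the entry cut-off of 20 makes the rule likely to fire for the CAPS endpoint. The cut-off truncates the Past Month entry score only; the Past Week endpoint has no cut-off. The second is that SCR could be tested raw. Section 9.4.1 rules that out, so only a further transformation or a change of test is open. The third is that the rule seriously inflates false positives. It does not if followed mechanically.

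**Conclusion.** The concern holds as an unspecified, data-dependent choice of scale and test, aimed at marginal distributions that the planned models do not require to be normal, and open to being made after unblinding. It should be changed.

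Its size is moderate. Type I error is 4.3-5.0% if the rule is applied mechanically and 6-7% per outcome under deliberate best-of-four selection. Power falls by about 10-18 points only if the fallback ignores baseline, and by about 2-3 if it uses it. The power figures rest on the assumed CAPS mean, SD, correlation, fall and effect. The normality check is also an assumption, since the plan names none. The frequency of firing for post-treatment CAPS cannot be stated: plausible inputs run from the nominal 5% to nearly always, driven by scores at 0.

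**What to change.** Delete the two sentences on transformation and distribution-free statistics from Section 9.4.6. In their place, state before unblinding:

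- CAPS Past Week is analysed on its original point scale, and SCR and BOLD on the scales fixed in 9.4.1, whatever the marginal distribution.
- One named repeated-measures model is primary for each outcome, for example an LMM with Time x Group, and it accounts for the baseline value. No baseline-adjusted model is specified at present, so this has to be written in.
- Diagnostics are applied to residuals only and do not change the primary analysis.
- A bootstrap or robust-variance result and a rank-based result are reported as labelled sensitivity analyses.

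The cost is SAP wording and one or two extra analysis runs. No visit, assessment or sample size changes.
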